## 6.2 Performance Variables

Topic	Area	Analyzed parameters	Time of evaluation
Ocular surface fluorescein staining test	Studied eye	- Fluorescein staining score of the cornea (grades 0 to 5) - Fluorescein staining score of the temporal conjunctiva (grades 0 to 5) - Fluorescein staining score of the nasal conjunctiva (grades 0 to 5) - Global score (0 to 15)	D0 / D28 / D90
		- Global score = 0 / Global score > 0	
Tear film break-up time (TFBUT)	Studied eye	- Mean value in tenths of second	D0 / D28 / D90
Schirmer test without anesthesia in 5 minutes	Studied eye	- Value in mm	D0 / D28
Global assessment of dry eye symptoms Each symptom separately	Both eyes globally	- Dryness sensation - Foreign body sensation - Burning sensation - Stinging sensation - Pruritus - Blurred vision - Sensitivity to light - Global Sum Score	D0 / D28 / D90
Ocular surface disease quality of life (OSD-QoL) questionnaire	-	Seven dimensions: - Daily activities - Difficulties with work and handicap - Giving up makeup - Acknowledgement of the disease - Acceptance of the disease - Fear for the future - Emotional well-being + 1 global question	D0 / D90

Methodology for OSD-QoL scores calculation

Dimension	Items	Maximum score
Daily activities	Q1 Q2 Q3 Q4 Q5	22
Handicap and Work Difficulties	Q6 Q7 Q8 Q9 Q10	22
Giving up Make-up	Q11	4
Acknowledgement of the disease	Q12 Q13	8
Acceptance of the disease	Q14	4
Fear for the future	Q15 Q16 Q17 Q18 Q19	20
Emotional Well-Being	Q20 Q21 Q22 Q23 Q24 Q25 Q26 Q27 Q28	27
Global Question	Q19	4

Each item is scored as stated in the questionnaire, a low score indicating a bad quality of life and high score a good quality of life.

For each dimension, a score will be computed as following

$$\text{Score} = \frac{\text{Sum of the items}}{\text{Max score for the dimension}} \times 100$$

In case of missing data or answer(s) « Not concerned », the score of the dimension will only be calculated if at least half of the items from the dimension are scored. The management of multiple answers will be described in the data entry guidelines and/or discussed during the masked review.

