APPENDIX B: METHODS OF CLINICAL EVALUATION

Any changes to the procedures described in this appendix will be provided under separate cover.

1. OCULAR SURFACE DISEASE-QUALITY of LIFE (OSD-QoL®) QUESTIONNAIRE

Subjects will be instructed to complete the OSD-QoL® questionnaire at Visits 2 and 5 or, in case of premature study discontinuation, at the time of withdrawal.

OSD-QoL® is a specific questionnaire for evaluating OSD symptoms impact on patients' health-related quality of life (HRQoL)²⁶. The Sponsor will provide OSD-QoL® to designated personnel at the site as part of the source documents, who will provide it to the subject for completion. The questionnaire includes 28 items divided into seven dimensions: "Daily activities," "Difficulties with work and handicap," "Giving up make-up," "Acknowledgement of the disease," "Acceptance of the disease," "Fear for the future" and "Emotional well-being."

OSD-QoL® is a validated and reliable instrument for measuring dry eye disease severity and impairment in HRQoL.

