### 3.4.2 Secondary Performance Endpoints

The secondary performance endpoints include the following:

- Mean CFB in the study eye at Visit 5 in total ocular surface fluorescein staining score
- Mean CFB in the study eye in fluorescein staining score for each area (corneal, nasal conjunctiva and temporal conjunctiva) at Visits 4 and 5
- Mean CFB in the study eye in TFBUT at Visits 4 and 5
- Evolution from baseline of Ocular Surface Disease-Quality of Life (OSD-QoL®) questionnaire scores at Visit 5 for all 7 dimensions: Daily Activities, Handicap and Work Difficulties, Giving up Make-up, Acknowledgement, Acceptance, Fear for the Future, and Emotional Well-Being. Analysis of the Global Question will also be reported.
- Mean CFB in the global sum score of dry eye symptoms at Visits 4 and 5: sensation of dryness, foreign body, burning, stinging, itching, blurred vision, sensitivity to light, each graded from 0 to 4
- Mean CFB in the study eye in volume of tear fluid secretion as assessed by the unanaesthetized Schirmer test at Visit 4
- Frequency of investigational eye drop instillations, as reported in subject diary

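### The SAP's OSD-QoL scoring table identifies the Global Question as Q19, an item number already used in the Fear for the future dimension

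*SAP*

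**What the plan says.** Protocol Appendix B, item 1, describes the instrument: "The questionnaire includes 28 items divided into seven dimensions". It does not mention a global question, and neither does the endpoint list in Protocol 7.1.2.

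The SAP adds one. SAP 3.4.2 repeats the seven-dimension endpoint and then states: "Analysis of the Global Question will also be reported". The performance-variable table in SAP 6.2 lists the seven dimensions and then, with a plus sign, "1 global question".

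The scoring table that follows in SAP 6.2 assigns item numbers and maximum scores. Three rows matter here:

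- the Fear for the future dimension, made up of "Q15 Q16 Q17 Q18 Q19" (five items, maximum 20);
- the last dimension, Emotional Well-Being, made up of "Q20 Q21 Q22 Q23 Q24 Q25 Q26 Q27 Q28" (nine items, maximum 27);
- "Global Question Q19 4" (one item, maximum 4).

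Q19 therefore appears in two rows. Neither document gives another number for the Global Question or says that one item is meant to serve both uses.

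**The concern.** A scoring table is an instruction to the programmer, and this one sends a single answer to two places. If the Global Question is a separate item, as the SAP's own list implies, the table points to the wrong variable. The Global Question result would then repeat one answer that already contributes to Fear for the future, and the real global answer would go unanalysed.

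The row matters because it is the only definition of the Global Question in either document. The question is absent from the protocol, and SAP section 4, which lists changes from the protocol's statistical section, does not mention it. Within these documents there is no second definition against which to catch the slip.

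**Working it through.** **Inputs.** Item lists and maxima come from the scoring table in SAP 6.2. The stated item count (28 in seven dimensions) comes from Protocol Appendix B.

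| Dimension | Items | Number of items | Maximum | Maximum / items |
|---|---|---|---|---|
| Daily activities | Q1 to Q5 | 5 | 22 | 4.4 |
| Handicap and work difficulties | Q6 to Q10 | 5 | 22 | 4.4 |
| Giving up make-up | Q11 | 1 | 4 | 4.0 |
| Acknowledgement | Q12, Q13 | 2 | 8 | 4.0 |
| Acceptance | Q14 | 1 | 4 | 4.0 |
| Fear for the future | Q15 to Q19 | 5 | 20 | 4.0 |
| Emotional well-being | Q20 to Q28 | 9 | 27 | 3.0 |

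**Step 1: reproduce the protocol's count.** 5 + 5 + 1 + 2 + 1 + 5 + 9 = 28. The 28 entries are all different and are exactly Q1 to Q28. The dimension rows therefore agree with the protocol, and no number up to Q28 is left over for a further item.

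**Step 2: test the two ways of resolving the duplicate.**

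- *Q19 is a fear item.* The dimensions hold 28 items, as the protocol says. The Global Question is additional, as SAP 6.2 says, and needs a number outside Q1 to Q28. The next free number would be Q29, but that is inference, because the questionnaire is not among the documents. Only the Global Question row has to change.
- *Q19 is the global item.* Fear for the future would shrink to Q15 to Q18, and the dimensions would hold 28 − 1 = 27 items. That contradicts the protocol's 28. The Fear row's item list would be wrong, and its maximum would have to be checked.

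The first resolution fits every other statement in the two documents. The second conflicts with one of them.

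**Step 3: see what the maxima add.** 20 / 5 = 4 for Fear for the future is compatible with Q19 belonging there. It is weak support, because the table gives only dimension totals. In two dimensions the average is 22 / 5 = 4.4, so if item maxima are whole numbers they differ within a dimension. An average of 4 does not fix the maximum of Q19 itself.

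**Step 4: trace the consequence.** With the table programmed as written and Q19 a fear item, all seven dimension scores use the right items. The Global Question output, and nothing else, is taken from the wrong item.

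**The case against.** The strongest reply is that the slip is likely to be noticed and matters little. The row is labelled Global Question, and SAP 6.2 has items scored as the questionnaire states, so a programmer with the instrument in hand has a second source. Protocol 7.6.1 has the SAP reviewed at the masked data review and finalised before the codes are broken. The Global Question is an SAP addition, and SAP 7.6 treats all secondary tests as informational. This all stands: a wrong result is possible, not certain, and it would be a minor one. It does not make the row correct, and the remedy is small.

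A second reply is that one misread digit in text taken from a PDF could create the duplicate. That cannot be excluded. Nothing in the row itself looks broken, but the source SAP should be looked at before anything is changed.

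A reader might also infer more: that the Fear for the future score is contaminated by the global item, that its maximum should be 16, and that up to 4 of its 20 points (20%) come from the wrong question. The documents do not support this. It requires Q19 to be the global item, which leaves 27 items in the dimensions against the protocol's 28, and it requires an item maximum for Q19 within the Fear row that the table does not give. For the same reason one cannot say that no range check would detect the slip, since item-level ranges are not stated.

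**Conclusion.** The concern holds in a limited form. Q19 is assigned twice in an operative scoring table, and the evidence favours an incorrect item number in the Global Question row. If the row is followed literally, the whole Global Question result is a relabelled fear item.

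The damage ends there. The seven dimension scores specified in the protocol appear correct as tabulated, and the primary endpoint, the non-inferiority decision and the sample size do not use this instrument.

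The conclusion rests on two assumptions: that the table row reads as shown in the source SAP, and that the protocol's count of 28 items within the dimensions is right. The questionnaire would settle both which row is wrong and what the correct number is.

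**What to change.** Before unmasking, compare the scoring table in SAP 6.2 with the questionnaire and give each item one place.

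- If the global question is a separate item, as the documents indicate, replace Q19 in the Global Question row with its true number and confirm the maximum of 4 for that item.
- Only if the questionnaire shows Q19 to be the global item, correct the Fear for the future item list and maximum instead, using the questionnaire's own item maxima. The missing-item rule for that dimension ("the score of the dimension will only be calculated if at least half of the items from the dimension are scored") would then mean at least 2 of 4 items rather than 3 of 5, and the count in Protocol Appendix B would need reconciling.

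Use the same mapping in the analysis program. On the favoured reading the cost is one table row and one program line. Making the change while the data are masked avoids a scoring change after the results are known.

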## 7.6 Secondary performance endpoint analyses

All secondary performance endpoint analyses will be performed on the ITT and PP populations. Results of statistical tests will be two-sided and given for information purpose only.

The secondary performance variables will be described by treatment group at each visit on raw values and on the changes / baseline D0.

The treatment groups will be compared at each post-baseline time using the same covariance model used to analyze the primary endpoint. The interaction Treatment x Baseline will be tested and removed from the model if not significant. If significant, the interaction will be kept in the model (a graphical representation of the interaction will be displayed) and the Treatment effect will be approximated by using the global average of observed D0 values (Note that in case of interaction, the Treatment effect cannot be properly interpreted). In addition, the distribution of the residuals of the analysis of variance will be tested: if the normality is not verified (Shapiro-Wilk test at the 1% threshold), the analysis will be performed on the ranks of the data (if analyses on ranks and on raw values lead to the same conclusions, only analysis on raw values will be given).

Depending on the distribution of the data (multinomial data such as global assessment of dry symptoms evaluations), a sensitivity analysis will be performed to compare both groups using a generalized linear model for multinomial data (SAS® Glimmix Procedure) with the value at baseline as covariate.

For the Ocular surface fluorescein staining test, the % of patients with a total score at 0 at D28 and D90 will be given with its 95% confidence interval.

Graphical representations by bar charts will be provided for dry eye symptoms and OSD-QoL dimension scores.

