## 7.12 Missing data

For subjects who discontinued the study early, analyses of change from baseline to endpoint for continuous variables will be based on the last non-missing post-baseline data (last observation carried forward data imputation methodology).

For safety data, if the causality assessment of an AE is missing, it will be imputed as “Probably” related to the investigational treatment. Likewise, if the severity is missing, the AE will be assessed as “Severe”.

Regarding diaries, missing data will be discussed during the masked review.

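### OSD-QoL scoring: with a fixed denominator and only a half-items rule, an unscored item in a multi-item dimension counts as a zero answer

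*SAP*

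**What the plan says.** SAP 6.2 gives one scoring formula for the OSD-QoL: the sum of the items divided by the "Max score for the dimension", times 100. A table beside it fixes one maximum per dimension. On direction and item scoring it says "Each item is scored as stated in the questionnaire, a low score indicating a bad quality of life". For missing or 'Not concerned' answers the only instruction is that "the score of the dimension will only be calculated if at least half of the items from the dimension are scored".

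Two sentences defer something to later, and neither covers this case:

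- SAP 6.2: "The management of multiple answers will be described in the data entry guidelines and/or discussed during the masked review".
- SAP 7.12: "Regarding diaries, missing data will be discussed during the masked review".

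The rest of SAP 7.12 deals with last observation carried forward after early discontinuation and with missing causality or severity of adverse events. Protocol 4.2 says only that OSD-QoL scores will be calculated, and Protocol Appendix B only describes the instrument.

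The OSD-QoL change at Visit 5 is a listed secondary endpoint (Protocol 7.1.2, SAP 3.4.2). Under SAP 7.6 the secondary variables "will be described by treatment group at each visit on raw values and on the changes / baseline D0", and "The treatment groups will be compared at each post-baseline time using the same covariance model used to analyze the primary endpoint". The same section says: "Results of statistical tests will be two-sided and given for information purpose only".

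**The concern.** The half-items rule says when a score is computed, not how. With nothing else to go on, the programmer applies the stated formula. An unscored item then adds 0 to the numerator while its points remain in the denominator. That is the same arithmetic as a zero answer, at the bad end of the scale. A subject who ticks 'Not concerned', a reply the SAP itself expects, is pushed towards poor quality of life by a question that does not apply.

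Three outputs are exposed: the raw dimension scores by arm, the changes from D0, and the covariance model, where the D0 score is also the covariate. An item unscored at only one of the two visits can create a change where there was none. The two single-item dimensions (Q11 and Q14) are not affected, because without the item no score is calculated.

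**Working it through.** **Inputs from the SAP 6.2 table.** The item counts are 5 + 5 + 1 + 2 + 1 + 5 + 9 = 28, which reproduces the 28 items in seven dimensions stated in Protocol Appendix B. Five dimensions have more than one item. The fewest items needed for a score is half the item count, rounded up.

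**Assumptions.** Item ranges are not in the documents. I assume whole-number item scores from 0, with 4 points per item in Fear for the future (20/5) and Acknowledgement (8/2), and 3 per item in Emotional Well-Being (27/9). In Daily activities and Handicap/Work, 22 points over 5 items cannot be equal whole numbers. For these I took all 11 whole-number splits of 22 with item maxima from 2 to 6.

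**Ceiling.** This is the highest score a subject can reach when items are unscored, = 100 × (dimension maximum − maxima of the unscored items) / dimension maximum.

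| Dimension | Items, maximum | Items needed | Ceiling, one unscored | Ceiling, most unscored allowed |
|---|---|---|---|---|
| Daily activities; Handicap/Work (each) | 5, 22 | 3 | 16/22 to 20/22 = 72.7 to 90.9 | 10/22 to 18/22 = 45.5 to 81.8 |
| Acknowledgement | 2, 8 | 1 | 4/8 = 50 | 50 |
| Fear for the future | 5, 20 | 3 | 16/20 = 80 | 12/20 = 60 |
| Emotional Well-Being | 9, 27 | 5 | 24/27 = 88.9 | 15/27 = 55.6 |

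**Error in one score.** Take Fear for the future with four items at 3 and the fifth unscored. If the fifth answer would have been x, the complete score is 100 × (12 + x)/20. The formula as written gives 12/20 = 60 for every x. Dividing by the maximum of the scored items gives 12/16 = 75.

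| x | Complete score | Error as written | Error with reduced denominator |
|---|---|---|---|
| 0 | 60 | 0 | +15 |
| 1 | 65 | -5 | +10 |
| 2 | 70 | -10 | +5 |
| 3 | 75 | -15 | 0 |
| 4 | 80 | -20 | -5 |

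**False change, item unscored at one visit.** A subject at 3 on all five Fear items at both visits has a complete score of 15/20 = 75 and a true change of 0. With one item unscored only at D90, the change is 60 − 75 = -15. With it unscored only at D0, it is 75 − 60 = +15. A reduced denominator gives 12/16 = 75 at the incomplete visit and a change of 0.

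**Same item unscored at both visits.** Let the other four items each gain 1 and the fifth gain g. The complete change is (4 + g)/20, that is +20 for g = 0 and +25 for g = 1. As written it is 4/20 = +20; with a reduced denominator it is 4/16 = +25. So for a missing answer, the change as written is wrong only if that item would itself have changed. For an item that never applied to the subject, the scale is simply compressed.

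**Arm mean.** If 1, 4 or 8 subjects in an arm of 42 (84/2) each carry a 15-point error in the same direction, the mean moves by 15/42 = 0.36, 60/42 = 1.43 or 120/42 = 2.86 points. With 33 per arm the shifts are 15/33 = 0.45, 60/33 = 1.82 or 120/33 = 3.64. The numbers of affected subjects are assumed and serve only to show scale.

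**The case against.** The best defence is that the SAP leaves a step unstated and does not deliberately zero-fill. It separates scored items from missing and 'Not concerned' ones and requires half to be scored, which would be an odd safeguard if 'Not concerned' were meant to count as the worst answer. The authors may have had proration in mind. That is possible, but the fixed maxima in the table point the other way. Even on the kinder reading, two programmers could differ by 15 points on the same record.

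Other objections stand in part:

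- Item scoring is referred to the questionnaire, which is not available here. It may carry its own rule, and we do not know which items offer 'Not concerned'. If only single-item dimensions do, that route has no effect. The gap in the SAP is certain; its practical consequence is not.
- For an item that does not apply, there is no complete score to compare with, so the error table fits missing answers only. The harm for such items is the lowered ceiling and compressed change.
- A reduced denominator is not always closer to the truth. In the example it is worse when the missing answer would have been 0 or 1. It is a standard convention with an assumption behind it, not a proven correction.
- The arm-mean shifts put every error in one arm, at one visit and in one direction. The rule applies to both arms alike, and no between-arm bias is shown.
- The tests on this endpoint are informational. That limits the weight of the point but does not make the reported scores right.

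**Conclusion.** The concern holds. As SAP 6.2 is written, an unscored item in any of the five multi-item dimensions has the effect of a zero answer. A missing item makes the score too low unless its answer would have been 0, and no incomplete dimension can reach 100. Under the stated item ranges, one unscored Fear item lowers that score by 0 to 20 points in the worked example and can produce a false change of 15 points in either direction. The most unscored items the rule allows cap Fear at 60, Acknowledgement at 50 and Emotional Well-Being at 55.6.

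The point concerns a secondary endpoint. The frequency of unscored items is unknown, and the primary non-inferiority conclusion does not depend on it. It should be corrected before unmasking, so that the scoring rule is not chosen with the treatment codes known.

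**What to change.** Amend SAP 6.2 before the treatment codes are broken:

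1. If the questionnaire's own scoring rule covers missing and 'Not concerned' items, cite it and use it.
2. Otherwise, set the denominator to the sum of the maximum scores of the items actually scored in that dimension, keep the half-items rule, and state that this assumes unscored items resemble scored ones.
3. In either case, tabulate the maximum of each item. Without it, nobody can prorate the two 22-point dimensions.
4. Report the number of unscored items by dimension, visit and arm.

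A separate query, with no error shown: Q19 appears both in Fear for the future and as the Global Question. Check the questionnaire and state whether the double use is deliberate or an item number is wrong.

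The cost is a few lines of SAP text, one table taken from the questionnaire and a small change to the scoring program. No new data are needed. Protocol 7.6.1 already provides for SAP review at the masked data review and finalisation before unmasking, so the change fits there.

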### 6.3 Safety Variables

Topic	Area	Analyzed parameters	Time of evaluation
Bio-microscopic examination	Each eye	
 
- Eyelid Erythema
 
- Eyelid Swelling
 
- Ocular Discharge
 
- Conjunctival Chemosis
 
- Conjunctival Hyperemia
 
- Corneal Erosion
 
- Corneal Edema
 
- Corneal Infiltrates
 
	D0 / D28 / D90
Visual acuity test	Each eye	
 
- LogMAR = -Log(Visual acuity decimal)
 
	D0 / D28 / D90
Adverse events	All body	
 
- At least one AE during the study
 
- At least one TEAE during the study
 
- At least one ADE during the study
 
- At least one serious AE during the study
 
- At least one serious TEAE during the study
 
- At least one serious ADE during the study
 
- At least one unanticipated serious ADE during the study
 
- At least one anticipated serious ADE during the study
 
	During all study
Adverse events	Ocular	
 
- At least one ocular AE during the study
 
- At least one ocular TEAE during the study
 
- At least one ocular ADE during the study
 
- At least one ocular TEAE related (possible, probable, certain) to the eye drops during the study
 
- At least one ocular TEAE related (possible, probable, certain) to the procedure during the study
 
- At least one serious ocular AE during the study
 
- At least one serious ocular TEAE during the study
 
- At least one serious ocular ADE during the study
 
- At least one unanticipated serious ocular ADE during the study
 
- At least one anticipated serious ocular ADE during the study
 
- Ocular AE description
 
	During all study

Topic	Area	Analyzed parameters	Time of evaluation
Adverse events	Non-ocular	
 
- At least one non-ocular AE during the study
 
- At least one non-ocular TEAE during the study
 
- At least one non-ocular ADE during the study
 
- At least one non-ocular TEAE related (possible, probable, certain) to the eye drops during the study
 
- At least one non-ocular TEAE related (possible, probable, certain) to the procedure during the study
 
- At least one serious non-ocular AE during the study
 
- At least one serious non-ocular TEAE during the study
 
- At least one serious non-ocular ADE during the study
 
- At least one unanticipated serious non-ocular ADE during the study
 
- At least one anticipated serious non-ocular ADE during the study
 
- Non-ocular AE description
 
	During all study
Device Deficiency (ART)	-	
 
- At least one DD
 
- DD description
 
	Before D0
Device Deficiency (Investigational product)	-	
 
- At least one DD
 
- DD description
 
	After D0

